6.3.9. Timing of Dose Administration

Pembrolizumab will be administered on an outpatient basis on Day 1 of each cycle after all procedures/assessments have been completed as detailed on the schedule of study assessments (Table 2).

Pembrolizumab will be administered via a 0.2-5µm in-line filter as a 30 minute IV infusion (treatment cycle intervals or infusion length may be increased due to toxicity as described in Section 6.3.3). Due to the variability of infusion pumps from site to site, a window of -5 minutes and +10 minutes is permitted (i.e., infusion time is 30 minutes: -5 min/+10 min). In addition, infusion length may be increased due to toxicity as described in Section 6.3.3.

6.3.10. Trial Blinding/Masking

This is an open-label trial; therefore, the Sponsor, investigator and participant will know the treatment being administered.

6.4. Concomitant Medications/Vaccinations (allowed & prohibited)

Medications or vaccinations specifically prohibited in the exclusion criteria are also not allowed during the trial. If there is a clinical indication for one of these or other prohibited medications or vaccinations then discontinuation from trial therapy may be required. The Investigator should discuss any questions regarding this with the CI/designee/RM-CTU. The final decision on any supportive therapy or vaccination rests with the investigator and/or the participant's primary physician. However, the decision to continue the participant on trial therapy schedule requires the mutual agreement of the Investigator, CI/ designee, and the participant.

6.4.1. Acceptable Concomitant Medications

All treatments that the investigator considers necessary for a participant's welfare may be administered at the discretion of the investigator in keeping with the standards of medical care. All concomitant medication will be recorded on the e-case report form (e-CRF) including all prescriptions, over-the-counter (OTC), herbal supplements, and IV medications and fluids. All concomitant medications received within 28 days before the first dose and until the safety follow up visit should be recorded.

6.4.2. Prohibited Concomitant Medications

Participants are prohibited from receiving the following therapies during the screening and treatment phase (including retreatment for post-complete response relapse) of this trial:

- Anti-cancer systemic chemotherapy or biological therapy
- Immunotherapy not specified in this protocol
- Radiotherapy not specified in this protocol
- Investigational agents other than pembrolizumab
- Palliative radiotherapy for symptom control
- Live vaccines within 30 days prior to the first dose of trial treatment and while participating in the trial.

Examples of live vaccines include, but are not limited to, the following: measles, mumps, rubella, chicken pox, yellow fever, rabies, BCG, and typhoid (oral) vaccine. Seasonal influenza vaccines for injection are generally killed virus vaccines and are allowed; however intranasal influenza vaccines (e.g. Flu-Mist®) are live attenuated vaccines, and are not allowed.

- Glucocorticoids for any purpose other than to modulate symptoms from an event of clinical interest of suspected immunologic etiology. The use of physiologic doses of corticosteroids may be approved after consultation with the CI/designee.

Participants who, in the assessment by the investigator, require the use of any of the aforementioned treatments for clinical management should be removed from the trial. Participants may receive other medications that the investigator deems to be medically necessary. The Exclusion Criteria describes other medications which are prohibited in this trial. There are no prohibited therapies during the Post-Treatment Follow-up Phase.

6.5. Rescue Medications & Supportive Care

6.5.1. Supportive Care Guidelines

Participants should receive appropriate supportive care measures as deemed necessary by the treating investigator including but not limited to the items outlined below:

6.5.1.1. Diarrhoea:

Participants should be carefully monitored for signs and symptoms of:

- Enterocolitis (diarrhoea, abdominal pain, blood or mucus in stool, with or without fever)
- Bowel perforation (peritoneal signs and ileus).

In symptomatic participants, infectious etiologies should be ruled out, and if symptoms are persistent and/or severe, endoscopic evaluation should be considered.

- In participants with severe enterocolitis (Grade 3):
 - Pembrolizumab will be **permanently discontinued** and treatment with systemic corticosteroids should be initiated at a dose of 1 to 2 mg/kg/day of prednisone or equivalent. When symptoms improve to Grade 1 or less, corticosteroid taper should be started and continued over at least 1 month.
- In participants with moderate enterocolitis (Grade 2):
 - Pembrolizumab should be **withheld** and anti-diarrhoeal treatment should be started. If symptoms are persistent for more than one week, systemic corticosteroids should be initiated (e.g., 0.5 mg/kg/day of prednisone or equivalent). When symptoms improve to Grade 1 or

less, corticosteroid taper should be started and continued over at least 1 month. Guidelines for continuing treatment with pembrolizumab can be found in Appendix 5.

- All participants who experience diarrhoea should be advised to drink liberal quantities of clear fluids. If sufficient oral fluid intake is not feasible, fluid and electrolytes should be substituted via IV infusion.

6.5.1.2. Nausea/vomiting:

Nausea and vomiting should be treated aggressively, and consideration should be given in subsequent cycles to the administration of prophylactic antiemetic therapy according to standard institutional practice. Participants should be strongly encouraged to maintain liberal oral fluid intake.

6.5.1.3. Anti-infectives:

Participants with a documented infectious complication should receive oral or IV antibiotics or other anti-infective agents as considered appropriate by the treating investigator for a given infectious condition, according to standard institutional practice.

6.5.1.4. Immune-related adverse events:

Please see Section 6.5.2 below regarding diagnosis and management of adverse experiences of a potential immunologic etiology.

6.5.1.5. Management of Infusion Reactions:

Acute infusion reactions (which can include cytokine release syndrome, angioedema, or anaphylaxis) are different from allergic/hypersensitive reactions, although some of the manifestations are common to both AEs. Signs and symptoms usually develop during or shortly after drug infusion and generally resolve completely within 24 hours of completion of infusion. Signs/symptoms may include: Allergic reaction/hypersensitivity (including drug fever); Arthralgia (joint pain); Bronchospasm; Cough; Dizziness; Dyspnea (shortness of breath); Fatigue (asthenia, lethargy, malaise); Headache; Hypertension; Hypotension; Myalgia (muscle pain); Nausea; Pruritis/itching; Rash/desquamation; Rigors/chills; Sweating (diaphoresis); Tachycardia; Tumour pain (onset or exacerbation of tumour pain due to treatment); Urticaria (hives, welts, wheals); Vomiting.

NCI CTCAE Grade	Treatment	Premedication at subsequent dosing
Grade 1 Mild reaction; infusion interruption not	Increase monitoring of vital signs as medically indicated until the participant is deemed medically stable in the opinion of	None

indicated; intervention not indicated	the investigator.	
Grade 2 Requires infusion interruption but responds promptly to symptomatic treatment (e.g., antihistamines, NSAIDS, narcotics, IV fluids); prophylactic medications indicated for < =24 hrs	
Stop Infusion and monitor symptoms.
 
Additional appropriate medical therapy may include but is not limited to:
 
 • IV fluids • Antihistamines • NSAIDS • Acetaminophen • Narcotics 
Increase monitoring of vital signs as medically indicated until the participant is deemed medically stable in the opinion of the investigator.
 
If symptoms resolve within one hour of stopping drug infusion, the infusion may be restarted at 50% of the original infusion rate (e.g. from 100 mL/hr to 50 mL/hr). Otherwise dosing will be held until symptoms resolve and the participant should be pre-medicated for the next scheduled dose.
 
Participants who develop Grade 2 toxicity despite adequate premedication should be permanently discontinued from further trial treatment administration.
	
Participant may be pre-medicated 1.5h (\pm 30 minutes) prior to infusion of pembrolizumab with:
 
Diphenhydramine 50 mg po (or equivalent dose of antihistamine).
 
Acetaminophen 500-1000 mg po (or equivalent dose of antipyretic).

Grades 3 or 4 Grade 3: Prolonged (i.e., not rapidly responsive to symptomatic medication and/or brief interruption of infusion); recurrence of symptoms following initial improvement; hospitalisation indicated for other clinical sequelae (e.g., renal impairment, pulmonary infiltrates) Grade 4: Life-threatening; pressor or ventilatory support indicated	
Stop Infusion.
 
Additional appropriate medical therapy may include but is not limited to:
 
 • IV fluids • Antihistamines • NSAIDS • Acetaminophen • Narcotics • Oxygen • Pressors • Corticosteroids • Epinephrine 
Increase monitoring of vital signs as medically indicated until the participant is deemed medically stable in the opinion of the investigator. Hospitalisation may be indicated.
 
Participant is permanently discontinued from further trial treatment administration.
	
No subsequent dosing

Appropriate resuscitation equipment should be available in the room and a physician readily available during the period of drug administration. For further information, please refer to the Common Terminology Criteria for Adverse Events v4.0 (CTCAE) at http://ctep.cancer.gov
		

Table 8: below shows treatment guidelines for participants who experience an infusion reaction associated with administration of pembrolizumab.

6.5.2. Supportive Care Guidelines for Immune-related Adverse Event (irAE) and Immune-related Events of Clinical Interest (irECI)

Immune-related Adverse events (IrAEs) may be defined as an adverse event of unknown etiology, associated with drug exposure and is consistent with an immune phenomenon. IrAEs may be predicted based on the

nature of the pembrolizumab compound, its mechanism of action, and reported experience with immunotherapies that have a similar mechanism of action. Special attention should be paid to AEs that may be suggestive of potential irAEs. An irAE can occur shortly after the first dose or several months after the last dose of treatment.

If an irAE is suspected, efforts should be made to rule out neoplastic, infectious, metabolic, toxin or other etiologic causes prior to labeling an adverse event as an irAE. Participants who develop a Grade 2 or higher irAE should be discussed immediately with the CI/designee.

Recommendations to managing irAEs not detailed elsewhere in the protocol;

irAE	Withhold/Discontinue pembrolizumab?	Supportive Care
Grade 1	No action	Provide symptomatic treatment
Grade 2	May withhold pembrolizumab	Consider systemic corticosteroids in addition to appropriate symptomatic treatment. Steroid taper should be considered once symptoms improve to Grade 1 or less and tapered over at least 4 weeks.
Grade 3 and Grade 4	Withhold pembrolizumab Discontinue if unable to reduce corticosteroid dose to < 10 mg per day prednisone equivalent within 12 weeks of toxicity	Systemic corticosteroids are indicated in addition to appropriate symptomatic treatment. May utilize 1 to 2 mg/kg prednisone or equivalent per day. Steroid taper should be considered once symptoms improve to Grade 1 or less and tapered over at least 4 weeks.
Please Note: If an irAE does not resolve or improve to ≤ Grade 1 within 12 weeks after last administration of pembrolizumab, study therapy discontinuation should be considered after discussion with a Merck Clinical Director via the RM-CTU trial manager..		

Table 9: General Approach to Handling irAEs

Details for managing specific irAEs are summarised below:

Immune-mediated pneumonitis

Monitor participants for signs and symptoms of pneumonitis. If pneumonitis is suspected, evaluate with radiographic imaging. Exclude other causes of pneumonitis, and manage treatment in accordance with the guidelines above. Administer corticosteroids, withhold pembrolizumab for moderate (Grade 2) pneumonitis, and permanently discontinue pembrolizumab for severe (Grade 3) or life-threatening (Grade 4) pneumonitis.

Immune-mediated colitis

Monitor participants for signs and symptoms of colitis. Exclude other causes of colitis, and manage treatment in accordance with the guidelines above. Administer corticosteroids, withhold pembrolizumab for moderate (Grade 2) or severe (Grade 3) colitis, and permanently discontinue pembrolizumab for life-threatening (Grade 4) colitis.

Immune-mediated hepatitis

Monitor participants for changes in liver function (at the start of treatment, periodically during treatment and as indicated based on clinical evaluation) and symptoms of hepatitis. Exclude other causes of hepatitis, and manage treatment in accordance with the guidelines above. Administer corticosteroids and, based on severity of liver enzyme elevations, withhold or discontinue pembrolizumab.

Immune-mediated nephritis

Monitor participants for changes in renal function. Exclude other causes of nephritis, and manage treatment in accordance with the guidelines above. Administer corticosteroids, withhold pembrolizumab for moderate (Grade 2), and permanently discontinue pembrolizumab for severe (Grade 3) or life-threatening (Grade 4) nephritis.

Immune-mediated endocrinopathies

Monitor participants for signs and symptoms of hypophysitis (including hypopituitarism and secondary adrenal insufficiency). Exclude other causes of hypophysitis, and manage treatment in accordance with the guidelines above. Administer corticosteroids, withhold pembrolizumab for moderate (Grade 2), withhold or discontinue pembrolizumab for severe (Grade 3) and for life-threatening (Grade 4) hypophysitis.

Monitor participants for hyperglycemia or other signs and symptoms of type 1 diabetes. Exclude other causes of diabetes. Administer insulin for type 1 diabetes, and withhold pembrolizumab in cases of severe hyperglycemia until metabolic control is achieved.

Thyroid disorders have been reported in participants receiving pembrolizumab and can occur at any time during treatment; therefore, monitor participants for changes in thyroid function (at the start of treatment, periodically during treatment and as indicated based on clinical evaluation) and clinical signs and symptoms of thyroid disorders. Administer corticosteroids, withhold pembrolizumab for severe (Grade 3) hyperthyroidism, and permanently discontinue pembrolizumab for life-threatening (Grade 4) hyperthyroidism. Treat symptoms of hyperthyroidism as appropriate. Isolated hypothyroidism may be managed with replacement therapy without treatment interruption and without corticosteroids. For participants with severe (Grade 3) or life-threatening (Grade 4) endocrinopathy that resolved and is controlled with hormone replacement, continuation of pembrolizumab may be considered.

Other immune-mediated adverse events

Across clinical studies with pembrolizumab in approximately 5000 participants, the following additional clinically significant, immune-mediated adverse reactions were reported in less than 1% of participants: uveitis and severe skin reactions.

In addition a set of irAEs have also been classified as immune-related events of clinical interest (irECI) a full list of these can be found in events of clinical interest guidance in Section 7.4. Participants with symptomatic irECIs should immediately stop receiving pembrolizumab and be evaluated to rule out non treatment related causes of the event. Overdose and liver toxicity irECIs irrespective of relationship to the study drug should be reported **within 24 hours** of the investigator being aware of the event to the Sponsor who will in turn notify MSD. If the irECI is determined to be associated please refer to Appendix 4 for the recommendations on the management of these irECIs. If the event is not considered to be associated with the study drug the physician should exercise individual clinical judgment on the event management based on the participant. Any additional questions of the collection or information on management of irECIs should be directed to the Sponsor.

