6.3.8. Dose Modification

Pembrolizumab will be withheld for drug-related haematological and non-haematological of toxicity \geq Grade 3 including laboratory abnormalities, and severe or life-threatening AEs as per Table 7 below.

Toxicity	Hold Treatment For Grade	Timing for Restarting Treatment	Treatment Discontinuation
Diarrhoea/Colitis	2-3	Toxicity resolves to Grade 0-1.	Toxicity does not resolve within 12 weeks of last dose or inability to reduce corticosteroid to 10 mg or less of prednisone or equivalent per day within 12 weeks.
	4	Permanently discontinue	Permanently discontinue
AST, ALT, or	2	Toxicity resolves to Grade 0-1	Toxicity does not resolve within 12 weeks of last dose.

Increased Bilirubin	3-4	Permanently discontinue (see exception below) ¹	Permanently discontinue
Type 1 diabetes mellitus (if new onset) or Hyperglycemia	T1DM or 3-4	Hold pembrolizumab for new onset Type 1 diabetes mellitus or Grade 3-4 hyperglycemia associated with evidence of beta cell failure.	Resume pembrolizumab when participants are clinically and metabolically stable.
Hypophysitis	2-4	Toxicity resolves to Grade 0-1. Therapy with pembrolizumab can be continued while endocrine replacement therapy is instituted	Toxicity does not resolve within 12 weeks of last dose or inability to reduce corticosteroid to 10 mg or less of prednisone or equivalent per day within 12 weeks.
Hyperthyroidism	3	Toxicity resolves to Grade 0-1	Toxicity does not resolve within 12 weeks of last dose or inability to reduce corticosteroid to 10 mg or less of prednisone or equivalent per day within 12 weeks.
	4	Permanently discontinue	Permanently discontinue
Hypothyroidism		Therapy with pembrolizumab can be continued while thyroid replacement therapy is instituted	Therapy with pembrolizumab can be continued while thyroid replacement therapy is instituted.
Infusion Reaction	3-4	Permanently discontinue	Permanently discontinue
Pneumonitis	2	Toxicity resolves to Grade 0-1	Toxicity does not resolve within 12 weeks of last dose or inability to reduce corticosteroid to 10 mg or less of prednisone or equivalent per day within 12 weeks.
	3-4	Permanently discontinue	Permanently discontinue
	3-4	Permanently discontinue	Permanently discontinue
Renal Failure or Nephritis	2	Toxicity resolves to Grade 0-1	Toxicity does not resolve within 12 weeks of last dose or inability to reduce corticosteroid to 10 mg or less of prednisone or equivalent per day within 12 weeks.

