All Other Drug-Related Toxicity²	3 or Severe	Toxicity resolves to Grade 0-1	Toxicity does not resolve within 12 weeks of last dose or inability to reduce corticosteroid to 10 mg or less of prednisone or equivalent per day within 12 weeks.
	4	Permanently discontinue	Permanently discontinue

Note: Permanently discontinue for any severe or Grade 3 drug-related AE that recurs or any life-threatening event.
¹ For participants with liver metastasis who begin treatment with Grade 2 AST or ALT, if AST or ALT increases by greater than or equal to 50% relative to baseline and lasts for at least 1 week then participants should be discontinued.
² Participants with intolerable or persistent Grade 2 drug-related AE may hold study medication at physician discretion. Permanently discontinue study drug for persistent Grade 2 adverse reactions for which treatment with study drug has been held, that do not recover to Grade 0-1 within 12 weeks of the last dose.

Table 8: Dose modification guidelines for drug-related adverse events

If the toxicity does not resolve to Grade 0-1 within 12 weeks after last infusion, trial treatment should be discontinued at the discretion of the investigator. Participants with a laboratory adverse event still at Grade 2 after 12 weeks may continue treatment in the trial only if asymptomatic and controlled. For information on the management of adverse events, see section 7.

Participants who experience a recurrence of the same severe or life-threatening event at the same grade or greater with re-challenge of pembrolizumab should be discontinued from trial treatment.

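### For a first drug-related Grade 3 enterocolitis or colitis that resolves, section 6.5.1.1 requires a permanent stop of pembrolizumab while the section 6.3.8 dose table permits restart, and no section expressly overrides 6.5.1.1

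*Combined protocol and SAP*

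**What the plan says.** Four places in the protocol tell sites what to do with pembrolizumab at Grade 3.

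- **Section 6.5.1.1 (Diarrhoea), severe enterocolitis (Grade 3):** "Pembrolizumab will be permanently discontinued and treatment with systemic corticosteroids should be initiated". No exception is given.
- **Section 6.3.8 (Dose Modification).** The opening sentence limits the rule to drug-related events: "Pembrolizumab will be withheld for drug-related haematological and non-haematological of toxicity". The relevant row reads "Diarrhoea/Colitis 2-3 Toxicity resolves to Grade 0-1", where the last entry falls under the column "Timing for Restarting Treatment". The criterion for stopping at Grade 2-3 is "Toxicity does not resolve within 12 weeks of last dose or inability to reduce corticosteroid to 10 mg or less"; the steroid limit is a daily prednisone-equivalent dose, also to be reached by 12 weeks. Grade 4 is a permanent stop. The note under the table adds a permanent stop for a Grade 3 drug-related event that recurs.
- **Section 6.5.2, immune-mediated colitis:** withhold at Grade 2 or 3, permanently discontinue at Grade 4. It also tells sites: "Exclude other causes of colitis, and manage treatment in accordance with the guidelines above".
- **Appendix 4, Colitis:** withhold at Grade 3, discontinue at Grade 4.

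Section 6.5.2 further says that an immune-related event of clinical interest judged to be associated with the drug is to be managed from Appendix 4.

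**The concern.** Re-dosing after a severe toxicity is both forbidden and permitted, depending on which section a site opens. A pharmacist or investigator working from the dose table could restart pembrolizumab after a resolved Grade 3 colitis. A colleague at another site working from the supportive care text would stop for good. Both would be following the protocol, and the first would be breaching another part of it. What is at stake is patient safety and consistent treatment across the planned 15 to 24 sites.

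**Working it through.** There is no figure to reproduce. The check sets the passages side by side.

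**1. Do they concern the same event?** Yes, for drug-related cases. Section 6.5.1.1 sits under the heading Diarrhoea and describes enterocolitis by diarrhoea, abdominal pain and blood or mucus in the stool. The 6.3.8 row is labelled Diarrhoea/Colitis. The section 7.4 table lists enterocolitis, colitis and diarrhoea together in its colitis group. A site cannot escape the conflict by choosing another label.

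**2. What does each require for a first Grade 3 event?**

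| Place | At onset | After resolution to Grade 0-1 |
|---|---|---|
| 6.5.1.1 | Permanent stop | Restart forbidden |
| 6.3.8 table and note | Hold | Restart permitted if criteria are met; permanent stop if a Grade 3 event recurs |
| 6.5.2, colitis | Withhold | No Grade 3 restart terms |
| Appendix 4, colitis | Withhold | No Grade 3 restart terms (its Grade 2 row does give them) |

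Of the four places, 1 forbids restart, 1 permits it and 2 give no restart terms (1 + 1 + 2 = 4).

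**3. Where exactly do they collide?** The collision needs a first drug-related Grade 3 event, resolution to Grade 0-1 within 12 weeks of the last dose, and a steroid dose brought down to 10 mg/day or less within 12 weeks. With all three met, the table permits restart and 6.5.1.1 forbids it. A recurrent Grade 3 event or a Grade 4 event is a permanent stop under the table, so neither creates this conflict.

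**4. Does anything set an order of precedence?**
- The Appendix 4 routing in 6.5.2 is the closest text. It is a cross-reference; it does not say that it displaces 6.5.1.1, and the Grade 3 row it leads to does not state restart terms.
- Section 6.5.1.4 sends immune-related events to 6.5.2, again without saying that 6.5.1.1 yields.
- Section 6.10.1 sends the reader to Section 6.2 for unacceptable adverse experiences, and 6.2 is the radiotherapy section.
- Section 6.5.1.1 itself points to an Appendix 5 for continuing treatment, under Grade 2 only, and the appendices end at 4.

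**5. Which way does the conflict run?** Dosing stops at onset under all four rules. Restart is allowed, never required, and 6.10.1 lets an investigator stop for unacceptable adverse experiences. Only a restart can breach a stated rule.

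**The case against.** The best defence is that the protocol does route the case. Grade 3 enterocolitis falls in the section 7.4 colitis group, 6.5.2 sends drug-associated events of that kind to Appendix 4, and Appendix 4 says withhold. In addition, 6.5.1 presents its items as supportive measures the investigator finds necessary, and 6.5.2 wants immune-related events of Grade 2 or higher discussed at once with the chief investigator or designee. All of this lowers the practical risk and stands to that extent. It does not remove the conflict: the 6.5.1.1 instruction is worded as mandatory, nothing displaces it, and the person consulted would be reading the same text.

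A reader might also infer more than the documents support:

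- **That 6.5.1.1 is simply the one section out of line with three that agree.** Only the 6.3.8 table permits restart at Grade 3. Section 6.5.2 and Appendix 4 say withhold and go no further, so they do not show which rule was intended.
- **That three rules compete for events unresolved at 12 weeks.** Beside the table criterion, the prose after it says "trial treatment should be discontinued at the discretion of the investigator", and a note in 6.5.2 says "study therapy discontinuation should be considered after discussion". That note belongs to a general table for immune-related events not covered elsewhere, and colitis is covered elsewhere. What remains is a table-versus-prose difference within 6.3.8 that spans many toxicities and is not specific to colitis.
- **That the differing steroid schedules strengthen the point.** At Grade 3 both 6.5.1.1 and Appendix 4 use prednisone 1 to 2 mg/kg/day, with an intravenous start added in the appendix. The lower Grade 2 dose in 6.5.1.1 is only an example. These differences do not bear on restart.
- **That exclusion criterion 7 settles the matter.** It bars entry after severe colitis from earlier immunotherapy; it does not address dosing on trial.

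**Conclusion.** The inconsistency is real, in current text, and narrow. It should be fixed. For a first drug-related Grade 3 enterocolitis or colitis that resolves within 12 weeks with steroids at 10 mg/day or less, the two dosing rules cannot both stand, and a site using the dose table can re-dose a patient whom 6.5.1.1 says must not be re-dosed.

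The documents give no incidence of Grade 3 colitis, so no number of affected patients is claimed. Alpha, power and sample size are unaffected. The conclusion rests on reading enterocolitis and diarrhoea/colitis as the same event, which section 7.4 supports, and on the absence of any express precedence rule in the protocol as supplied. Appendix 4 also refers to a separate guidance document that is not among the documents. Which Grade 3 rule is right is a clinical decision that this review does not make.

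**What to change.** Limit the change to diarrhoea/colitis. The clinical team confirms one Grade 3 rule and uses it in section 6.3.8, section 6.5.1.1, the colitis text of section 6.5.2 and the colitis rows of Appendix 4.

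- **Option A (hold, then decide).** Replace the Grade 3 discontinuation wording in 6.5.1.1 with: *Pembrolizumab will be withheld; restart or permanently discontinue per the Diarrhoea/Colitis row of the section 6.3.8 table, and permanently discontinue if a Grade 3 event recurs.* Add the same pointer to the Grade 3 colitis text in 6.5.2 and Appendix 4.
- **Option B (stricter).** Keep 6.5.1.1. Change the 6.3.8 row to hold at Grade 2 and permanently discontinue at Grade 3-4, and change the Grade 3 colitis text in 6.5.2 and Appendix 4 to match.

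Do not resolve this by declaring that the 6.3.8 table governs every toxicity. Appendix 4 discontinues pembrolizumab for Grade 3 neurologic events. The 6.3.8 table has no neurologic row, and its row for all other drug-related toxicity allows restart after Grade 3, so a blanket rule would relax a stricter safety instruction.

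Clerical, in the same amendment: in 6.5.1.1 change Appendix 5 to Appendix 4; in 6.10.1 change Section 6.2 to Section 6.3.8.

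Cost: a wording amendment and a short memo to sites. Data collection, analysis and sample size do not change.
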